Spain	BIFAP	
Adequate number of individuals with the diagnosis of interest
 
Suitable denominator population for population-level rates
 
Adequate information regarding mortality is captured
	Primary care	EHR	22m	7,900	31/03/2023

Country	Name of Database	Justification for Inclusion	Health Care setting	Type of Data	Number of active subjects	Feasibility count of disease (ILD)*	Data lock for the last update
		Contribute to geographical diversity of data sources included					
France	CDW Bordeaux	
Adequate number of individuals with the diagnosis of interest
 
Adequate information regarding mortality is captured
 
Contribute to geographical diversity of data sources included
	Secondary care	EHR	2.4m	3,900	16/11/2023
Germany	IQVIA DA Germany	
Adequate number of individuals with the diagnosis of interest
 
Suitable denominator population for population-level rates
 
Contribute to geographical diversity of data sources included
	Primary care and outpatient secondary care	Claims	43m	8,800	23/01/2024

\*Counts for ILD overall (not for the different subtypes). The feasibility assessment with counts for the different conceptids has been added in the appendix. Rounded up to the nearest hundred.

Clinical Practice Research Datalink GOLD, United Kingdom (University of Oxford)

	D2.2.3 - Study Protocol for P3-C1-005	
	Author(s): [name] [name]	Version: V2.1
	Dissemination level: Public	

The Clinical Practice Research Datalink (CPRD) GOLD is a database of anonymised electronic health records (EHR) from General Practitioner (GP) clinics in the UK that use the Vision® software system for their management.(Herrett, Gallagher et al. 2015) The source population encompasses 98% of the UK, registered with GPs responsible for non-emergency care and referrals. Participating GPs provide CPRD EHR for all registered patients who did not specifically request to opt out of data sharing. Covering 4.6% of the current UK population, GOLD includes 4.9% of contributing GP practices, providing comprehensive information within its defined source population. GOLD contains data from all four UK constituent countries and the current regional distribution of its GP practices is 5.7% in England, 55.6% in Scotland, 28.4% in Wales, and 10.2% in Northern Ireland (May 2022).

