## 8.5 Study Population with inclusion and exclusion criteria

### Population-level descriptive epidemiology

All patients with an incident diagnosis of ILD in the period 1st of January 2010 to 31st of December 2022 (or latest date available). Notably, all patients need to have at least 365 days of data visibility (except for CDWBordeaux) prior to the date of their first diagnosis and no prior diagnosis of ILD. This requirement of at least 1 year of prior data history will not hold for children <1 year of age.

	D2.2.3 - Study Protocol for P3-C1-005	
	Author(s): [name] [name]	Version: V2.1
	Dissemination level: Public	

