**Table 5. Operational Definitions of Inclusion Criteria.**

Criterion	Details	Order of application	Assessment window	Care Settings 	Code Type	Diagnosis position 	Applied to study populations:
Observation period in the database during the period 2010-2022 (or the latest date available)	All individuals present in the period 2010-2022 (or the latest date available)	After	n/a	IP, OP, OT	n/a	n/a	All individuals within selected databases
Prior database history	Study participants will be required to have 365 days of prior history observed before contributing observation time	Prior	[-365, -1]	OP	n/a	n/a	All individuals within CPRD GOLD, BIFAP and IQVIA DA Germany
Washout period	Individuals newly diagnosed with ILD will be required not to have a diagnosis of ILD any time prior to the diagnosis of ILD	Prior	[-inf, -1]	OP	n/a	n/a	All individuals diagnosed with ILD

 IP = inpatient, OP = outpatient, ED = emergency department, OT = other, n/a = not applicable

 Specify whether a diagnosis code is required to be in the primary position (main reason for encounter)

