46270493	3.28661E+14	Interstitial lung disease of childhood			Yes	
42539090	737184001	Interstitial lung disease with systemic vasculitis			Yes	

Concept ID	Concept Code	Concept Name	Alveolitis/ Pneumonitis	Lung fibrosis	Unspecified ILD	Drug-induced ILD*
4273378	64667001	Interstitial pneumonia	Yes			
3655969	870573008	Interstitial pneumonia with autoimmune features	Yes			
600563	1017197007	Interstitial pulmonary fibrosis due to inhalation of drug		Yes		Yes
600562	1017196003	Interstitial pulmonary fibrosis due to inhalation of substance		Yes		
4218175	416916004	Lipoid pneumonitis	Yes			
4124539	233730002	Lupus pneumonia	Yes			
45768902	707433009	Lymphangioliomyomatosis due to tuberous sclerosis syndrome		Yes		
4195014	44274007	Lymphoid interstitial pneumonia	Yes			
434975	25897000	Malt-workers' lung	Yes			
4229303	88687001	Manganese pneumonitis	Yes			
438175	86638007	Maple-bark strippers' lung	Yes			
4230447	40640008	Massive silicotic fibrosis of lung		Yes		
4121294	233751004	Metal pneumoconiosis		Yes		
4119445	233758005	Mica pneumoconiosis		Yes		
4137769	32139003	Mixed dust pneumoconiosis		Yes		
4119446	233759002	Mixed mineral dust pneumoconiosis		Yes		
433233	52333004	Mushroom workers' lung	Yes			
4006973	111292008	Necrotizing sarcoid granulomatosis			Yes	
45771019	707435002	Neuroendocrine cell hyperplasia of infancy			Yes	
4121295	233755008	Nickel pneumoconiosis		Yes		
4044215	129452008	Nonspecific interstitial pneumonia	Yes			
4124537	233698001	Paprika splitters' lung	Yes			
258564	60125001	Perinatal interstitial emphysema			Yes	
37208102	4.60561E+14	PF-ILD-progressive fibrosing interstitial lung disease		Yes		
259044	40122008	Pneumoconiosis		Yes		

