**Table S1.B. Excluded concept ids for ILD**

Concept ID	Concept Code	Concept Name	Domain	Vocabulary
42598655	3.36791E+14	Atypical interstitial pneumonia of cattle	Condition	SNOMED Veterinary
4146744	30042003	Confluent fibrosis of lung	Condition	SNOMED
4262577	361196000	Idiopathic hilar fibrosis	Condition	SNOMED
4120272	233726000	Localized pulmonary fibrosis	Condition	SNOMED
36716112	721977007	Lung fibrosis, immunodeficiency, 46,XX gonadal dysgenesis syndrome	Condition	SNOMED
4173590	50196008	Perialveolar fibrosis of lung	Condition	SNOMED
4148685	3514002	Peribronchial fibrosis of lung	Condition	SNOMED
258335	90117007	Tuberculous fibrosis of lung	Condition	SNOMED
36674196	770760006	16q24.1 microdeletion syndrome	Condition	SNOMED
4195694	67782005	Acute respiratory distress syndrome	Condition	SNOMED
3661406	6.74814E+17	Acute respiratory distress syndrome due to disease caused by Severe acute respiratory syndrome coronavirus 2	Condition	SNOMED
42598655	3.36791E+14	Atypical interstitial pneumonia of cattle	Condition	SNOMED Veterinary
37116655	733453005	Congenital nephrotic syndrome, interstitial lung disease, epidermolysis bullosa syndrome	Condition	SNOMED
3655347	860890006	Fetal interstitial neoplasm of lung	Condition	SNOMED
440748	77690003	Interstitial emphysema of lung	Condition	SNOMED
4084955	240629003	Malarial shock lung	Condition	SNOMED
440431	46970008	Mycoplasma pneumonia	Condition	SNOMED
4294404	76090006	Pittsburgh pneumonia	Condition	SNOMED
4110506	195896004	Pneumonia due to pleuropneumonia-like organism	Condition	SNOMED
4232327	89687005	Postimmersion-submersion syndrome	Condition	SNOMED
4148529	35037009	Primary atypical interstitial pneumonia	Condition	SNOMED
1340509	OMOP5166164	Progression of acute respiratory distress syndrome	Condition	OMOP Extension
438791	196115007	Pulmonary congestion and hypostasis	Condition	SNOMED
44783638	697923008	Pulmonary hypertension in lymphangioleiomyomatosis	Condition	SNOMED

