**Table S2 Feasibility person counts for ILD per database**

concept_id	concept_name	BIFAP	CDW Bordeaux	CPRD GOLD	IQVIA - DA Germany
4119786	Interstitial lung disease	7900	3900	6900	8800
253506	Pneumonitis	100	100	2200	100
253797	Post-inflammatory pulmonary fibrosis	10600		1000	
256036	Hemorrhagic varicella pneumonitis	200			
258564	Perinatal interstitial emphysema	100	100		100
260434	Acute radiation pneumonitis	300		300	600
435853	Pulmonary alveolar proteinosis	100		100	
437313	Rheumatic pneumonia	100			
438782	Idiopathic pulmonary hemosiderosis	100		100	
439298	Bronchitis and pneumonitis due to chemical fumes	300	100	100	1200
440748	Interstitial emphysema of lung	800		200	
444084	Extrinsic allergic alveolitis	2300	100	1900	5000
3655088	Pneumonitis caused by inhalation of oil	200		100	
3655110	Pneumonitis caused by fumes	100			
3655111	Pneumonitis caused by vapors	200			
4025168	Diffuse interstitial pulmonary fibrosis	300		7300	
4028118	Diffuse interstitial rheumatoid disease of lung			200	
4044215	Nonspecific interstitial pneumonia	600			
4045227	Respiratory bronchiolitis associated interstitial lung disease	100		200	
4089507	Toxoplasma pneumonitis				100
4110180	Pneumonitis due to inhalation of vomitus			500	
4110182	Acute drug-induced interstitial lung disorder	200	100	100	200
4112678	Acute pneumonitis due to chemical fumes			100	
4112681	Chronic pulmonary fibrosis due to chemical fumes			100	
4112809	Aspiration pneumonitis due to anesthesia during labor and delivery				100
4112813	Drug-induced interstitial lung disorder	100		200	200
4112814	Chronic drug-induced interstitial lung disorders	100		100	100

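### Perinatal interstitial emphysema counts as ILD while interstitial emphysema of lung is excluded, with no stated reason; this may affect the under-18 stratum materially

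*Protocol*

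**What the plan says.** Appendix I states that each concept ID was reviewed and then placed in an inclusion or an exclusion list.

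- Table S1.A (included) has concept 258564, "Perinatal interstitial emphysema", ticked only as unspecified ILD.
- Table S1.B, titled "Excluded concept ids for ILD", has concept 440748, "Interstitial emphysema of lung".
- Table S2 gives the feasibility row "Perinatal interstitial emphysema 100 100 100". The three figures belong to BIFAP, CDW Bordeaux and IQVIA DA Germany; the CPRD GOLD cell is blank.
- The footnote to Table 3, which points to these appendix counts, says "Rounded up to the nearest hundred".

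On entry of infants, section 8.5 (population-level part) says: "This requirement of at least 1 year of prior data history will not hold for children <1 year of age". Table 5 says "Study participants will be required to have 365 days of prior history observed before contributing observation time" and applies this to CPRD GOLD, BIFAP and IQVIA DA Germany without an infant exemption. Section 8.4 and the patient-level part of section 8.5 do not mention the exemption either. CDWBordeaux needs no prior history.

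Under-18 is a prespecified age category (section 8.6.3). Section 8.8.3 assigns incidence to BIFAP, CPRD GOLD and IQVIA DA Germany, and survival to BIFAP, CPRD GOLD and CDWBordeaux.

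**The concern.** The two lists put the general interstitial emphysema concept outside ILD and the perinatal one inside it, and nothing in Appendix I explains the split. An oversight is plausible, because the lists contain at least one other unreconciled entry: concept 42599152 stands in both Table S1.A and Table S1.B.

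The consequence falls in one place. By its name, the perinatal concept can only add cases under 18 years. Across all ages such cases are lost in the total. The under-18 stratum is reported separately, though, so part of its incidence rate or median survival could describe a newborn condition whose general form the protocol has ruled out as ILD. A reader using that stratum as background for signal assessment could not see this.

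**Working it through.** The protocol states no under-18 case count, so there is no figure of its own to reproduce. The size can only be shown as a range.

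**Inputs**
- k, perinatal cases: at most 100 in BIFAP, CDWBordeaux and IQVIA DA Germany (Table S2). With rounding up, each 100 can mean 1 to 100. The rounding is stated under Table 3; I assume that it also holds for Table S2, where every count is a multiple of 100.
- N, other cases: the row "Interstitial lung disease 7900 3900 6900 8800" (BIFAP, CDW Bordeaux, CPRD GOLD, IQVIA DA Germany) counts a single concept, 4119786. Table S1.A also includes concept 4187218, inhaled-substance pneumonitis, with 49,500 persons in BIFAP, 12,200 in CDW Bordeaux and 12,400 in IQVIA DA Germany. Taken alone, that concept gives a floor for the cohort without any question of overlap between concepts.
- s, share of other cases aged under 18: not in the protocol. **Assumption:** 1% to 3%.

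**Formula:** perinatal share of the under-18 stratum = k / (k + s × N).

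**At k = 100, with 4187218 alone as N**

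| Database | s = 3% | s = 1% |
|---|---|---|
| BIFAP | 100/(100 + 1,485) = 6% | 100/(100 + 495) = 17% |
| CDWBordeaux | 100/(100 + 366) = 21% | 100/(100 + 122) = 45% |
| IQVIA DA Germany | 100/(100 + 372) = 21% | 100/(100 + 124) = 45% |

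**At k = 100, with all other included Table S2 concepts summed** (85,900; 16,500; 28,600; an upper bound, since one person may carry several codes)

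| Database | s = 3% | s = 1% |
|---|---|---|
| BIFAP | 100/(100 + 2,577) = 4% | 100/(100 + 859) = 10% |
| CDWBordeaux | 100/(100 + 495) = 17% | 100/(100 + 165) = 38% |
| IQVIA DA Germany | 100/(100 + 858) = 10% | 100/(100 + 286) = 26% |

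**Lower counts, 4187218 as N.** At k = 50 the share is 50/1,535 = 3% to 50/545 = 9% in BIFAP and 50/416 = 12% to 50/172 = 29% in CDWBordeaux. At k = 5 it is at most 5/500 = 1% in BIFAP and 5/127 = 4% in CDWBordeaux.

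**Majority threshold.** At k = 100, perinatal cases exceed half of the stratum only if s is below 100/49,500 = 0.20% (BIFAP), 100/12,200 = 0.82% (CDWBordeaux) or 100/12,400 = 0.81% (IQVIA DA Germany).

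**All ages.** Even against the single concept 4119786, the most is 100/7,900 = 1.3%, 100/3,900 = 2.6% and 100/8,800 = 1.1%. Against the 4187218 floor it is 0.2%, 0.8% and 0.8%.

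**Which results are exposed.** Combining Table S2 with section 8.8.3: BIFAP for incidence and survival, CDWBordeaux for survival only, IQVIA DA Germany for incidence only, CPRD GOLD for neither. If the 365-day rule is applied as written in section 8.4 and Table 5, newborn records stay out of the primary care databases and only entry through CDWBordeaux is certain.

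**The case against.** The two entries are separate concept IDs, and Appendix I says that each was reviewed. Table S1.A also holds other early-life concepts, such as pulmonary fibrosis of prematurity and neuroendocrine cell hyperplasia of infancy, so including a perinatal concept may be deliberate. This stands in part: the protocol does not prove an error, and it does not settle clinically whether the condition belongs to ILD. It does not explain why the general concept is excluded, and that missing reason is the point made here.

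The size is also uncertain. The numerator is known only as 1 to 100, the child share is assumed, and Table S2 does not say whether its counts are limited to 2010-2022 or to eligible first diagnoses. All of this stands, which is why only a range is given.

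A reader might go further and infer that perinatal emphysema dominates the under-18 results. Using 7,900 and 3,900 as the cohort size with the same 1-3% would give 100/337 = 30% to 100/179 = 56% in BIFAP, and 100/217 = 46% to 100/139 = 72% in CDWBordeaux. The protocol does not support this, because those totals count one concept, not the ILD cohort. Once concept 4187218 is counted, no database reaches a majority in the 1-3% range, even at the maximum of 100.

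**Conclusion.** The concern holds in limited form. The two concept lists treat related concepts in opposite ways without a stated reason, and every resulting case falls in the under-18 overall-ILD stratum. At the maximum count the share may be material: about 6-17% in BIFAP and 21-45% in each of CDWBordeaux and IQVIA DA Germany. These figures rest on an assumed 1-3% child share and on concept 4187218 alone as the cohort floor. They shrink if the true count is below 100 or the cohort is larger.

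The alveolitis/pneumonitis, lung fibrosis and drug-induced analyses are not affected, and the all-ages results hardly move. Entry of newborn records into the primary care databases also depends on which statement of the prior-history rule governs. This is a minor point that is cheap to settle.

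**What to change.** 1. Reconcile Tables S1.A and S1.B. Either treat both concepts alike, by moving 258564 to Table S1.B in line with 440748, or keep 258564 with a stated reason and report the under-18 overall-ILD stratum with and without it.
2. Reconcile the infant exemption in section 8.5 with section 8.4 and Table 5, and say whether it also covers the patient-level analyses.

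Cost: one line in the concept list, or one additional run of a single stratum in the affected databases, plus a sentence in each of the sections that state the history rule.

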**D2.2.3 - Study Protocol for P3-C1-005**

**Author(s):** [name] [name]

**Version:** V2.1

**Dissemination level:** Public

Concept ID	Concept Code	Concept Name	Alveolitis/ Pneumonitis	Lung fibrosis	Unspecified ILD	Drug-induced ILD*
37205802	785345002	Pneumoconiosis caused by sisal dust		Yes		
254389	17996008	Pneumoconiosis due to inorganic dust		Yes		
442125	805002	Pneumoconiosis due to silica		Yes		
256146	426853005	Pneumoconiosis due to silicate		Yes		
4249010	73144008	Pneumoconiosis due to talc		Yes		
253506	205237003	Pneumonitis	Yes			
3655110	846629004	Pneumonitis caused by fumes	Yes			
3655088	840728005	Pneumonitis caused by inhalation of oil	Yes			
3655111	846630009	Pneumonitis caused by vapors	Yes			
256721	64030005	Pneumonitis due to inhaled solid	Yes			
4187218	415126001	Pneumonitis due to inhaled substance	Yes			
4226132	405569006	Post-radiotherapy pneumonitis	Yes			
4215594	80614003	Prolonged pulmonary alveolitis	Yes			
435853	10501004	Pulmonary alveolar proteinosis (PAP)	Yes			
37109889	723829000	Pulmonary fibrosis, hepatic hyperplasia, bone marrow hypoplasia syndrome		Yes		
45768996	707551007	Pulmonary interstitial glycogenosis			Yes	
4174275	277844007	Pulmonary lymphangioleiomyomatosis			Yes	
4086243	24369008	Pulmonary sarcoidosis			Yes	
4266525	62371005	Pulmonary siderosis		Yes		
4221865	84004001	Radiation pneumonitis	Yes			
4045227	129451001	Respiratory bronchiolitis associated interstitial lung disease	Yes			
437313	7548000	Rheumatic pneumonia	Yes			
4184896	54867000	Rheumatoid fibrosing alveolitis		Yes		
4162539	398640008	Rheumatoid pneumoconiosis		Yes		
4120265	233700005	Rodent handlers' lung	Yes			

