### Objectives

**Objective 1:** to measure the incidences of ILD and the incidence of ILD subtypes (alveolitis/pneumonitis excluding aspiration and infectious pneumonitis), lung fibrosis and drug induced ILD), stratified by age, sex and calendar time.

**Objective 2:** to characterise the patients with ILD by age, sex, comorbidities and concomitant medication. This analysis will be done for the overall ILD group and for the following ILD-subtypes (alveolitis/pneumonitis excluding aspiration and infectious pneumonitis), lung fibrosis and drug induced ILD).

**Objective 3:** to measure the survival rates in patients diagnosed with ILD and to measure survival rates within the following ILD-subtypes (alveolitis/pneumonitis (excluding aspiration and infectious pneumonitis), lung fibrosis and drug induced ILD). Survival rates will be stratified by age, sex and calendar time

Description of the proposed objectives to be achieved in the study is displayed in **Table 1**.

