Main measure of effect:	
Incidence rates, expressed as number of individuals newly diagnosed with ILD per 100,000 person-years. Incidence rates will be calculated overall and stratified by sex, age (age category) and calendar time (year). Incidence rates will be calculated for ILD overall and for the following ILD subtypes: alveolitis/pneumonitis (excluding aspiration and infectious pneumonitis), lung fibrosis and drug induced ILD.
 
Median survival time in patients with newly diagnosed ILD stratified by sex, age-category, and calendar time. If numbers are sufficient, survival rates will not only be done for the overall group but also for the following ILD subtypes: alveolitis/pneumonitis (excluding aspiration and infectious pneumonitis), lung fibrosis and drug induced ILD.

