### Patient-level characterisation

The study cohort will include all individuals registered in the database between 1st of January 2010 and 31st of December 2022, with at least 365 days of data visibility (except for CDWBordeaux) and a new ILD diagnosis.

The concept definition of ILD and ILD-subtypes is described in Table S1, [Appendix I](#). The operational definitions of the inclusion and exclusion criteria are presented by means of [Table 5](#) and [Table 6](#), respectively.

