4311410	86294001	Pneumonitis due to inhalation of essence	Condition	SNOMED
4112683	196034005	Pneumonitis due to inhalation of milk	Condition	SNOMED
4112839	196033004	Pneumonitis due to inhalation of regurgitated food	Condition	SNOMED
4110180	196035006	Pneumonitis due to inhalation of vomitus	Condition	SNOMED
442297	57463004	Pneumonitis due to inhaled liquid	Condition	SNOMED
255735	35339003	Primary pneumonic plague	Condition	SNOMED
42572644	3.36161E+14	Pulmonary abscess due to Rhodococcus	Condition	SNOMED Veterinary
4138244	32204007	Pulmonary actinobacillosis	Condition	SNOMED
258354	187052004	Pulmonary African histoplasmosis	Condition	SNOMED
4077129	17993000	Pulmonary arteritis	Condition	SNOMED
4296039	76846002	Pulmonary endarteritis	Condition	SNOMED
4102140	28122003	Pulmonary eosinophilic granuloma	Condition	SNOMED
4345699	240387006	Pulmonary glanders	Condition	SNOMED
46269691	1.01401E+14	Pulmonary granuloma	Condition	SNOMED
4119928	233742007	Pulmonary hyalinizing granuloma	Condition	SNOMED
44783637	697921005	Pulmonary hypertension in sarcoidosis	Condition	SNOMED

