**D2.2.3 - Study Protocol for P3-C1-005**

**Author(s):** [name] [name]

**Version:** V2.1

**Dissemination level:** Public

concept_id	concept_name	BIFAP	CDW Bordeaux	CPRD GOLD	IQVIA - DA Germany
4112839	Pneumonitis due to inhalation of regurgitated food			100	
4119796	Toxic pneumonitis	200			
4140472	Drug-induced pneumonitis	100			
4148529	Primary atypical interstitial pneumonia	100			
4187218	Pneumonitis due to inhaled substance	49500	12200	500	12400
4195014	Lymphoid interstitial pneumonia	100		100	
4218175	Lipoid pneumonitis			100	
4221865	Radiation pneumonitis	200			
4226132	Post-radiotherapy pneumonitis	100			
4236182	Interstitial pulmonary fibrosis of prematurity			100	
4236725	Pulmonary fibrosis due to and following radiotherapy	100			
4273378	Interstitial pneumonia	200		1300	
4306082	Aspiration pneumonitis	3100		7800	
4311555	Desquamative interstitial pneumonia	100			
4341520	Acute interstitial pneumonia	300			
36714118	Cryptogenic organizing pneumonia	800		500	
37208102	PF-ILD-progressive fibrosing interstitial lung disease				
45763749	Idiopathic interstitial pneumonia	1300			
45763750	Idiopathic pulmonary fibrosis	9100		4300	
45771019	Neuroendocrine cell hyperplasia of infancy	100			
46272927	Interstitial lung disease due to connective tissue disease			100	
46274046	Chemical pneumonitis caused by anesthesia	100	200		100

	D2.2.3 - Study Protocol for P3-C1-005	
	Author(s): [name] [name]	Version: V2.1
	Dissemination level: Public	

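### A generic inhalation code kept in alveolitis/pneumonitis cannot separate out the aspiration the subtype excludes, and it dominates that subtype's feasibility counts in three of four databases

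*Protocol*

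**What the plan says.** The objectives name the subtypes as "alveolitis/pneumonitis (excluding aspiration and infectious pneumonitis), lung fibrosis and drug induced ILD" (Table 1 in Section 7). Section 8.5 makes the appendix list operative: "The concept definition of ILD and ILD-subtypes is described in Table S1". The introduction to Appendix I says every concept was reviewed for inclusion or exclusion.

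- **Table S1.A (included)** lists 4187218, "Pneumonitis due to inhaled substance", among the descendants and marks it as alveolitis/pneumonitis.
- **Table S1.B (excluded)** lists "Aspiration pneumonitis" (4306082), "Pneumonitis due to inhaled liquid" (442297), and the concepts for inhaled vomitus, milk and regurgitated food. It does not list 4187218.
- **Table S2 (feasibility person counts)** gives, in the order BIFAP, CDWBordeaux, CPRD GOLD, IQVIA DA Germany, "4187218 Pneumonitis due to inhaled substance 49500 12200 500 12400". The row for the ILD concept itself is "4119786 Interstitial lung disease 7900 3900 6900 8800".

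Section 8.8.3 assigns incidence (objective 1) to BIFAP, CPRD GOLD and IQVIA DA Germany, characterisation (objective 2) to all four databases, and survival (objective 3) to BIFAP, CPRD GOLD and CDWBordeaux. Section 11 repeats that IQVIA DA Germany is not used for survival.

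**The concern.** The subtype is meant to leave out aspiration. The specific aspiration concepts are removed, but a broader concept remains whose name covers any inhaled substance. Where a database records aspiration under the broad concept, the exclusion does not reach those records. How far this happens would depend on local coding, so the same definition could describe different diseases in different databases.

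Section 6 says the study should guide the assessment of signals of drug-induced ILD. Rates and patient profiles for overall ILD and for alveolitis/pneumonitis would be a poor background for that purpose if one non-specific concept made up most of them in some databases and almost none in another.

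The study-size statement does not reveal the issue. The figures given there as ILD counts, 3,900 to 8,800, come from one concept only.

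**Working it through.** **Inputs.** Each Table S2 row was classed by Tables S1.A and S1.B as alveolitis/pneumonitis, lung fibrosis, unspecified ILD or excluded, then summed by database. Blank cells were read as zero.

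**The plan's own figure.** The stated ILD counts of 7,900, 3,900, 6,900 and 8,800 (Table 3; range in Section 8.7) are reproduced exactly, but only as the single row 4119786. They are not the sum of the concepts that the study will treat as ILD. In BIFAP the generic concept alone is 49,500/7,900 = 6.3 times that figure; in CDWBordeaux 12,200/3,900 = 3.1 times; in IQVIA DA Germany 12,400/8,800 = 1.4 times.

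**Shares.** Share = count of 4187218 divided by the sum over included concepts.

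| | BIFAP | CDWBordeaux | CPRD GOLD | IQVIA DA Germany |
|---|---|---|---|---|
| 4187218 | 49,500 | 12,200 | 500 | 12,400 |
| Alveolitis/pneumonitis sum | 57,800 | 12,600 | 8,200 | 19,800 |
| Same, without 4187218 | 8,300 | 400 | 7,700 | 7,400 |
| Share of subtype | 85.6% | 96.8% | 6.1% | 62.6% |
| All included ILD sum | 86,000 | 16,600 | 28,000 | 28,700 |
| Same, without 4187218 | 36,500 | 4,400 | 27,500 | 16,300 |
| Share of overall ILD | 57.6% | 73.5% | 1.8% | 43.2% |

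**Rounding.** Counts are rounded up to the next hundred. Allowing for this, the subtype shares lie in 85.6–89.5%, 96.8–100%, 5.0–7.7% and 62.4–64.9%. The overall shares lie in 57.5–59.8%, 73.3–76.2%, 1.4–2.0% and 43.0–44.6%.

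**Overlap.** A person can carry several concepts. Suppose everyone with another listed concept also has 4187218. The people who enter only through 4187218 then number at least its count minus the rest:

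- Subtype: 49,500 − 8,300 = 41,200 (BIFAP); 12,200 − 400 = 11,800 (CDWBordeaux); 12,400 − 7,400 = 5,000 (IQVIA DA Germany).
- Overall ILD: 49,500 − 36,500 = 13,000 (BIFAP); 12,200 − 4,400 = 7,800 (CDWBordeaux). For IQVIA DA Germany, 12,400 − 16,300 is negative, so there is no lower bound above zero.

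**Concepts without a row.** Many Table S1.A concepts have no row in Table S2 and were counted as nothing. The same differences show how many people those concepts would have to add, without overlap, before 4187218 lost its majority: for example 41,200 in the BIFAP subtype and 13,000 in BIFAP overall ILD.

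**Where aspiration is recorded.** The excluded aspiration concept has 3,100 in BIFAP and 7,800 in CPRD GOLD, and is blank in CDWBordeaux and IQVIA DA Germany. The generic concept exceeds 12,000 in those two and is only 500 in CPRD GOLD, so the pattern reverses. The main alternative contents have their own rows. The fume, vapour and oil concepts total 800 in BIFAP, 100 in CDWBordeaux, 300 in CPRD GOLD and 1,200 in IQVIA DA Germany. Extrinsic allergic alveolitis has 2,300, 100, 1,900 and 5,000. In CPRD GOLD, which uses the specific concepts, aspiration, vomitus and regurgitated food total 7,800 + 500 + 100 = 8,400, against 300 for fume, vapour and oil (28 to 1).

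**The case against.** The strongest reply is that the protocol nowhere says what is recorded under 4187218. No source codes are given, and the name also covers causes that Table S1.A keeps on purpose (fumes, vapours, oil, solids). The concept list was reviewed, so keeping this one may have been a decision. In BIFAP, the database with the largest count, the excluded concept holds 3,100 people, so the exclusion does remove people there. This stands as far as it goes. A reader might infer that the 49,500, 12,200 and 12,400 are aspiration cases, or that the exclusion fails entirely outside CPRD GOLD. The documents do not support that: the evidence is indirect, and it is weaker for BIFAP than for the two databases with blank cells.

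The counts are also feasibility counts. They are not stated to be limited to first diagnoses in 2010–2022 with a year of history, so they show scale and not the final cohorts. Results are reported by database without pooling (Section 8.9), Section 11 warns of uneven recording, and the planned CohortDiagnostics package can show index-event misclassification. None of this removes the problem. No action is tied to the diagnostic, and the warning does not mention this concept.

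The reply does not supply a reason to keep, in the main definition, a concept that cannot distinguish what the objective excludes.

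**Conclusion.** The point holds as a code-list defect that should be resolved before execution. It is clearest for alveolitis/pneumonitis, where 4187218 is the majority of summed counts in BIFAP, CDWBordeaux and IQVIA DA Germany and about 6% in CPRD GOLD. For overall ILD it is the majority in BIFAP and CDWBordeaux. A reader might extend that to IQVIA DA Germany, but there it is the largest single concept at 43%, not a majority.

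The reach differs by database: BIFAP on objectives 1 to 3, IQVIA DA Germany on objectives 1 and 2, CDWBordeaux on objectives 2 and 3. It would be wrong to read it as affecting all three objectives in all three databases. Lung fibrosis and drug-induced ILD do not contain this concept, so their definitions are untouched; in particular, the drug-induced ILD rate is not inflated by it.

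The sizes rest on Table S2: person counts rounded up, overlap ignored, blanks and unlisted concepts taken as zero. That the generic concept carries aspiration is a strong inference for CDWBordeaux and IQVIA DA Germany. The actual share cannot be computed from the protocol for any database.

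**What to change.** Before execution, move 4187218 from Table S1.A to Table S1.B. Enter it there explicitly: it is listed among the descendants, so deleting the line alone could let it return through a parent. Exclude the exact concept only, so that the specific fume, vapour and oil concepts stay in. Report one sensitivity analysis of overall ILD and alveolitis/pneumonitis with 4187218 restored.

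Check 256721 (inhaled solid) for consistency with the excluded inhaled-liquid concept. A reader might conclude that it must go too, but Table S2 has no count for it and nothing in the protocol requires its removal.

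The change is one line in the code list and one extra run. It loses genuine non-aspiration inhalation pneumonitis coded only generically, in a number the protocol does not give. It also leaves a summed count of at most about 400 for the listed subtype concepts in CDWBordeaux, so stratified subtype results there would be sparse.
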